1.2 Prostate Cancer

Prostate cancer is the most common cancer in men in Australia and the USA. Each year, close to 3000 men in Australia die of prostate cancer and around 18,700 new cases are diagnosed. According to the Australian Institute for Health and Welfare (AIHW), there were 56,158 new cases of cancer diagnosed in males in 2005, by far the most common being prostate cancer (16,349 cases), which made up over 29% of all diagnoses [4]. As life expectancy increases, so will the incidence of this disease, thus creating possibly significant public health issues.

Prostate cancer is clinically a heterogenous disease characterized by biologic behaviour that ranges between indolent and aggressive states. The exact molecular basis for the observed disease heterogeneity is not well understood. Ultrasound (US) is used in prostate imaging for diagnostic purposes and to provide image guidance for biopsies. Prostate biopsies are performed by transrectal US (TRUS), which allows systematic sampling of the gland. Most initial biopsies involve the removal of 6–12 cores with equal distributions from base to apex and right and left sides, as well as preferential lateral sampling [5]. This widespread sampling directly targets the peripheral zone,

Clinical Study Protocol, Study No AVP0458-01-001, Amendment 4, 23rd October 2012 Page 16 of 46

which is the origin for > 70% of prostate cancers. Although TRUS is used to visualise the gland and perform systematic biopsies, the detection rate of prostate cancer with TRUS is 20%–40% in men with clinical suspicion of the disease, there are a significant number of false negatives, TRUS has a low ability to distinguish between benign and malignant nodules, and patients face repeated biopsies and rising PSA levels [6]. Doctors may recommend an anaesthetic for the biopsy and a course of antibiotics before or afterwards. Even when cancers are detected, the size of the tumour is often underestimated by TRUS. The discomfort and cost of the procedure further limit its role in screening.

There are several treatments available for localised prostate cancer and they include active surveillance (watchful waiting); surgery with a radical prostatectomy; radiation, including conformal external beam radiotherapy, brachytherapy with seeds and high dose rate brachytherapy; high intensity focused ultrasound; and hormone therapy, which is used to shrink the prostate and the tumour prior to radiotherapy. If the prostate cancer has already spread to other organs or to bone at the time of diagnosis, hormone therapy becomes the primary method of treatment. Most advanced prostate cancers respond well to hormone therapy and can do so for several years.

1.3 AVP0458

1.3.1 TAG-72 Antigen

Tumour associated glycoprotein-72 (TAG-72) is a pancarcinoma antigen that was initially identified in cancer tissues by its immunoreactivity to the mouse monoclonal antibody B72.3. TAG-72 antigen is a high molecular weight glycoprotein that is expressed on adenocarcinomas of the breast, stomach, colon, prostate, and ovary [7-9]. The murine monoclonal antibody (mAb) CC49 specifically recognizes TAG-72 and has a higher affinity for this antigen and lower immunogenicity than B72.3. The higher affinity of CC49 has been shown to result in better tumour localization [10, 11] [12].

1.3.1.1 Expression of TAG-72 in prostate cancer

Expression of TAG-72 in prostatic adenocarcinomas has been evaluated using the CC49 antibody [13-15]. The study performed by Brenner and colleagues [13] reported that approximately 80% of prostatic adenocarcinomas express TAG-72, with most immunoreactivity observed in the cytoplasm of malignant cells and no immunoreactivity within benign epithelium or stroma. CC49 staining was detected in all well differentiated tumours tested (n=6; Gleason score of 2-4), 8 of 10 moderately differentiated (Gleason score of 5 to 6), and 7 of 9 poorly differentiated tumours (Gleason score of 7 to 9). In contrast to primary lesions, expression of TAG-72 in metastatic prostate cancers is downregulated, but still present in 50% of the bone lesions tested [13]. Only 50% of the specimens from men treated with androgen deprivation were immunoreactive (10 of 20, vs 21 of 25 non-hormonally treated tumours), likely due to the changes in glandular mucin triggered by hormonal therapy. However, in a more recent study, Hong et al (2011) found that TAG-72 is strongly positive in the majority of prostate cancers irrespective of grade, stage or pre-operative PSA [41].

Expression of TAG-72 in ovarian cancer

Several studies evaluated the expression of TAG-72 in ovarian cancer tissue samples and microarrays of different stages and histological subtypes [16, 17]. The study conducted by Ponnusamy and colleagues found four patterns of TAG-72 localization: cytoplasmic, membrane bound, luminal and diffused (both membrane and cytoplasmic) [17]. A total of 88% of the ovarian cancer tissue samples (n=43) showed immunoreactivity with the CC49 antibody, and expression of TAG-72 in advanced stage cancer tissues was significantly higher (p=0.035) compared to the early stage tumours. The study also reported that membrane localization of TAG-72 in tumours was significantly (p=0.0082) associated to the poor clinical outcome, while cytoplasmic staining was correlated significantly to a better prognosis (p=0.0051).

Similarly, the study conducted by Chauhan and colleagues demonstrated that 72% of all ovarian cancer types showed immunolabelling for TAG-72 [16]. Expression levels of TAG-72, MUC1 and CA125 antigens were significantly higher in advanced stage carcinomas compared with early stage (p<0.005). Of the 48 epithelial ovarian cancer samples, 87.5% of all cases were TAG-72 positive.

1.3.1.3 Clinical evaluation of anti-TAG-72 antibodies

Antibodies recognizing TAG-72 have been assessed in numerous Phase I/II clinical trials with modest results [11, 18-21]. Most clinical trials made use of radiolabelled whole antibody for radioimmunotherapy or radioimmunoguided surgery and have employed a pre-targeting strategy. Haematological toxicity most often limited the quantity of radionuclide that could be administered, whereas the amount of radiation delivered to tumour sites was still below that required to cause tumour regressions.

These clinical results clearly define the need for a recombinant anti- TAG-72 antibody fragment with improved pharmacokinetics (PK), faster blood clearance and significantly higher dose deposition.

Antibody based cancer therapy and radioimmunodetection

Numerous antibody-based cancer therapies have been developed in the past decades, taking advantage of the specificity and relatively easy production of antibodies. Antibodies are also the basis of other cytotoxic pharmaceutical products, such as radiolabelled antibodies for radioimmunotherapy [22], immunotoxins, chemotherapy/antibody conjugates [23], cytokine/antibody conjugates [24], and others.

Although antibody therapeutics provide significant benefit to some patients with cancer, they are seldom curative. Antibody conjugation to cytotoxic drugs enhances the antitumor activity of antibodies and reduces the systemic toxicity of the conjugated drugs [25]. By linking monoclonal antibodies to highly cytotoxic drugs, higher tumour selectivity is conferred to the drugs that are otherwise too toxic to be used on their own and may confer greater therapeutic utility compared to using monoclonal antibodies alone.

Radioimmunodetection of tumour sites may provide additional information on the stage of disease, and can also provide in-vivo evidence of expression of antigen by tumour, and subsequent likely response to targeted monoclonal antibody therapeutic approaches.

1.3.3 Recombinant Diabodies

Avibody[™] products are antibody-like proteins designed and created by *Avipep Pty Ltd* (Parkville, Victoria). They are multimeric antibody fragments (diabodies, triabodies) that represent an improved alternative to antibodies [26-30], as they are characterized by increased tissue penetration, high avidity (slow off-rates) and fast blood clearance. These characteristics have been demonstrated in several animal models, in which Avibody proteins have shown excellent tumour localization [31-35].

Avibody products can be created, like intact antibodies, with at least two target binding regions, which enables them to attain very high affinity for the target antigen (e.g. cancer cells). Significant improvements in Avibody products compared with the parent Ig are:

- Tumour: blood ratios of 50:1 after 12 hours for diabodies
- Lack of Fc components and thus, undesirable effector functions (toxicity) for some clinical indications
- Reduced immunogenicity
- Small size (60~120kDa), ideal for tumour/clot targeting in vivo.

Avibody products are suitable for further customization of their *in vivo* properties by conjugating clinically relevant payloads (radioisotopes for imaging or with cytotoxic drugs for therapy) in a site-specific manner and with defined stoichiometry. Among the clinically relevant payloads that could be accommodated by Avibody products are imaging and fluorescent probes, and radiotracers for Positron Emission Tomography (PET) or Single Photon Emission Computed Tomography (SPECT) imaging, radiotracers for therapy and toxins or drugs for other therapeutic modalities. For therapeutics, Avipep's conjugation strategies can be associated to multiple novel linker chemistries designed to optimally deliver payloads, depending on whether or not the targeted tumour antigen internalizes.

Avipep has focused on the use of Avibody products in the diabody format, 55 kDa noncovalent scFv dimers formed by producing scFv molecules with short (4-5 amino acid) linkers between their variable heavy (V_H) and variable light (V_L) chains [36, 37]. This prevents the V_H and V_L chains in a molecule from creating a typical scFv orientation. Instead, V_L from one molecule associate with V_H from another, resulting in the formation of a rigid dimer that divalently interacts with antigen.

1.3.4 AVP0458 Drug Description

AVP0458 targets the pancarcinoma antigen TAG-72 described above in **Section 1.3.1**. The recombinant 51 kDa AVP0458 that is being evaluated in this clinical study was designed to contain the already clinically validated antibody sequence of the TAG-72 specific CC49 antibody (variable region). Two of the CC49 functional binding sites are fused in sequence to form a stable, biologically active diabody. The amino acid sequence of the variable domains of CC49 has been modified [38] in order to achieve a high-expressing and highly stable recombinant molecule.

In order to increase its hydrodynamic size, AVP0458 was PEGylated (24 PEG residues were added on specific Cysteine residues). PEGylation of a drug or pharmaceutical agent prolongs their

circulatory time by reducing renal clearance. The molecular weight of the PEGylated AVP0458 (PEG-AVP0458) is ~56kDa.

Biodistribution of 124I-PEG-AVP0458 in LS174T Xenograft Model

The biodistribution properties and PET imaging characteristics of ¹²⁴I-PEG-AVP0458 have been evaluated in nude mice with the TAG-72-expressing LS174T colorectal cancer xenografts. Excellent tumour uptake (mean peak uptake 55%ID/gm at 24-48 hrs post injection) was observed, with prolonged tumour retention, and excellent imaging properties. Normal tissues showed minimal 124I-PEG-AVP0458 uptake, consistent with blood pool activity only. Pharmacokinetic analysis revealed a long serum half-life, with $T\%\alpha$ =6.77 hrs, and $T\%\beta$ =29.72 hrs. This data supports the use of PEG-AVP0458 as a specific targeting strategy for TAG-72 expressing tumours.

1.4 **Rationale for the Study**

The TAG-72 antigen has been shown to be a well defined, clinically relevant target for monoclonal antibody based therapy. Avibody[™] technology has been shown to be an exciting approach to modifying antibodies to enhance tumour uptake and penetrance, and pegylation of diabodies has been shown to eliminate renal uptake and enhance pharmacokinetics. PEG-AVP0458 has been engineered to specifically target TAG-72 expressing tumours, including prostate and ovarian cancer, in both laboratory and in-vivo animal model systems. To confirm the tumour targeting potential of PEG-AVP0458, a Phase I first-in-human clinical trial is proposed to explore the safety, biodistribution and pharmacokinetics, and immunogenicity, of a single dose of ¹²⁴l-labelled PEG-AVP0458 in patients with prostate or ovarian cancer

STUDY OBJECTIVES

2.1 Primary Objective

The primary objective of this clinical study is to evaluate the safety of a single dose of ¹²⁴I-PEG-AVP0458 in patients with prostate and ovarian cancer.

2.2 Secondary Objectives

The secondary objectives of this study are to evaluate the biodistribution, including tumour targeting, PK and immunogenicity of ¹²⁴I-PEG-AVP0458 in patients with prostate and ovarian cancer.

3 STUDY DESIGN

3.1 Summary of Design

This is a Phase I, open-label study of the safety and biodistribution of two escalating doses of PEG-AVP0458, labelled with 3-5 mCi of ¹²⁴I for PET imaging. A schematic diagram of the trial is presented in Protocol Synopsis, page 7. ¹²⁴I-PEG-AVP0458 is to be administered to patients by slow intravenous infusion over an hour, with safety monitoring during and for 4 hours post infusion. PET imaging will be performed post infusion of ¹²⁴I-PEG-AVP0458 on Day 0, and on a further 4 occasions over a one week period. The PEG-AVP0458 dose will be either 1 mg/m² (in the first dose level) or 10 mg/m² (second dose level), and the amount of ¹²⁴I radioactivity is kept constant at 3-5 mCi. The last dose group will receive either of these two doses, depending on safety and the quality of imaging results obtained in the dose-escalation part of the study; this will be determined in the interim analysis. The dose groups can be summarised as follows:

Dose Group	Number of Patients	PEG-AVP0458 dose (mg/m²)	¹²⁴ I-PEG-AVP0458 dose (mCi)
1	3	1	3-5
2	3	10	3-5
3	6	1 or 10	3-5

The choice of the two doses of PEG-AVP0458, 1 mg/m² and 10 mg/m², was based on the amount of AVP04-07 diabody used in the biodistribution studies in mouse xenografts [39] and on the amount of TAG-72 intact antibody (CC49) tested in previous clinical trials [11]. Prior trials of CC49 showed that optimal tumour uptake and biodistribution occurred at approximately 10mg dose levels. Results of a 14-day single dose toxicology study of PEG-AVP0458 have shown the no-adverse effect level (NOAEL) to be 20mg/kg, which corresponds to dose that is approximately 100 times the starting dose of 1mg/m² in this protocol (when normalised to body surface area). In view of the anticipated lack of toxicity of PEG-AVP0458, and prior experience with murine CC49 in patients, escalation from 1mg/m² to to the second dose level of 10mg/² is considered appropriate to define the optimal biodistribution and tumour uptake dose level.

The primary endpoint of the study is the safety of a single dose of PEG-AVP0458. The secondary endpoints measured are biodistribution, PK and immunogenicity of ¹²⁴I-PEG-AVP0458.

Eligible patients with TAG-72-positive ovarian or prostate cancer will be entered into the study sequentially at each site until the total targeted number for each dose level is reached.

As this is a first in-human study, a single subject will receive the first dose of ¹²⁴I-PEG-AVP0458. Further dose administration will be sequential within each cohort to mitigate risks of anaphylactic or any other acute unexpected reactions. Administration of doses within a cohort will be staggered by 24 hours, i.e. there will be a period of 24 hours between the first, second and subsequent subjects in a cohort to observe and interpret reactions and adverse events. This time frame is sufficient to exclude any possible acute allergic or anaphylactic reactions to PEG-AVP0458.

After completion of accrual into the first cohort (1 mg/m 2 dose), the Trial Management Committee will review the safety data from these participants before a decision is made to escalate the dose to 10 mg/m 2 .

If no patients entered in the 1^{st} dose group experience a dose-limiting toxicity (DLT), and the Trial Management Committee agree, then the 2^{nd} dose group may commence on the higher dose of 10 mg/m^2 30 days after the last patient on the first dose group has received the 124 I-PEG-AVP0458 infusion. If any one patient in either cohort of 3 patients experiences a DLT, then 3 additional patients will be entered in that dose group. If additional patients are treated in the 1^{st} dose group, all patients entered must have been observed for 30 days before a new patient may receive an infusion in the 2^{nd} dose group. If greater than or equal to two DLTs are observed at a dose, then the MTD is considered to have been exceeded.

If at most, one DLT is observed, the next 3 patients are assigned to the next highest dose. If two or more DLTs are observed, then the MTD is considered to have been exceeded.

A DLT is defined as any of the following events occurring within 30 days of study drug administration:

- Any Grade 2 or greater allergic reaction.
- Any Grade 3 toxicity. Exceptions are: fever; asymptomatic hyperglycemia; hypophosphatemia; nausea, vomiting, or diarrhoea despite the use of optimal supportive medical therapy; leukopenia or thrombocytopenia that revert to baseline within three weeks of occurrence; lymphopenia without other dose-limiting events (eg opportunistic infection).
- Any Grade 4 toxicity.

The 30 days will allow identification and mitigation of the risks of any delayed immunogenic reaction before progressing to a subsequent cohort.

In the event 2 or more patients experience DLT at the first dose level, an additional 3 patients will be entered at a 0.5mg/m² dose level.

After the last evaluation of the last patient enrolled in the second dose group (10 mg/m²), an interim analysis of the safety and dosimetry data will be undertaken. This analysis will be considered by the Trial Management Committee to ascertain which of the two doses, 1 or 10 mg/m², produces the better safety profile and dosimetry results for PEG-AVP0458. The dose selected will be based on imaging characteristics and pharmacokinetic data of ¹²⁴I-PEG-AVP0458 at each dose level. This chosen dose will be used to infuse the last 6 patients in the second part of the clinical study. This last group will enrol 3 patients with prostate cancer and 3 with ovarian cancer and will continue to evaluate safety as the primary endpoint.

Because of the low PEG-AVP0458 doses tested in this study, the fact that only two dose levels are being evaluated, and the past clinical experience with the intact parent antibody (CC49), this study is not expected to identify a maximum tolerated dose. It should be noted that the tracer dose of ¹²⁴I-labelled to PEG-AVP0458 has not been reported to be associated with adverse events in prior clinical trials of ¹²⁴I-labelled compounds.

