3.2 Sample Size

An anticipated total of 12-18 patients will be entered into the study. In the dose-escalating part of the study, 6 patients with either prostate or ovarian cancer will be enrolled: 3 in the 1 mg/m² dose group and 3 in the 10 mg/m² dose group. If DLTs occur, the number will increase to a maximum of 12.

In the second part of the study, a further 6 patients will be enrolled, 3 with ovarian cancer and 3 with prostate cancer. They will receive the PEG-AVP0458 dose defined in the interim analysis.

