5.3 Administration of Investigational Product

The appropriate quantities of 124 I-PEG-AVP0458 will be drawn into a syringe with sterile sodium chloride injection and 5% human serum albumin (HSA). The resultant 124 I-PEG-AVP04 in the syringe will be injected into a 100 mL infusion bag of sterile sodium chloride injection and 5% HSA via a sterile 0.2 μ m filter.

Patients will receive 1 mg/m² or 10 mg/m² of ¹²⁴I-PEG-AVP0458 infusion intravenously over approximately 1 hour. Patients will be kept reclined during the infusion and observed for the first four hours after the infusion has been completed.

PEG-AVP-0458 will be labelled with ¹²⁴I in laboratories of the Ludwig Institute of Cancer Research, at Austin Health, under sterile conditions and according to SOPs (see Section 9.3). Following QC testing, the dose of 124 I-PEG-AVP-0458 will be then distributed to the infusion room at the study site for subsequent patient infusion. The criteria for dose escalation and dose selection are provided in Section 5.14.

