5.10 Criteria for Dose Escalation and Dose Selection

The Trial Management Committee is responsible for decisions regarding dose escalation (moving dose group 1 to group 2) and dose selection (moving from group 2 to 3), based on safety and dosimetry data.

For dose escalation, the decision is based on safety. If no patients in dose group 1 experience a DLT, then dose group 2 may commence 30 days after the last patient on the dose group 1 has received the PEG-AVP0458 infusion.

If any one patient in either cohort of 3 patients experiences a DLT, then 3 additional patients will be entered in that dose group. If additional patients are treated in the dose group 1, all patients entered must have been observed for 30 days before a new patient may receive an infusion in dose group 2. If greater than or equal to two DLTs are observed at a dose, then the MTD is considered to have been exceeded. If at most, one DLT is observed, the next 3 patients are assigned to the next highest dose. If two or more DLTs are observed, then the MTD is considered to have been exceeded.

In the event 2 or more patients experience DLT at the first dose level, an additional 3 patients will be entered at a 0.5mg/m² dose level

The Trial Management Committee will evaluate safety and dosimetry data available after the dose escalation part of the study (Interim Analysis) and determine the dose to be administered to the last 6 patients in the study.

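### The 0.5 mg/m² level opened after two DLTs at 1 mg/m² has no workable continuation: every dose written for the last six patients is one declared above the MTD, or higher

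*Protocol*

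**What the plan says.** Sections 3.1 and 5.10 of the protocol share the same escalation rules. One DLT among three patients adds three patients to that dose group. On stopping, 3.1 says: "If greater than or equal to two DLTs are observed at a dose, then the MTD is considered to have been exceeded". On continuing: "If at most, one DLT is observed, the next 3 patients are assigned to the next highest dose". If the two DLTs occur at the first level, "an additional 3 patients will be entered at a 0.5mg/m² dose level". The schema in the synopsis repeats this step.

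For the third dose group, 3.1 says "The last dose group will receive either of these two doses", meaning 1 or 10 mg/m². The dose table in 3.1, its paragraph on the interim analysis, and 8.4 give the same two options. Section 5.3 states "Patients will receive 1 mg/m² or 10 mg/m²", and 9.3 describes preparation for those two amounts only. Both 3.1 and 8.4 place the interim analysis after the 10 mg/m² cohort.

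Two places are worded more openly. Section 3.2 says of the last six patients "They will receive the PEG-AVP0458 dose defined in the interim analysis", and 5.10 has the Trial Management Committee "determine the dose to be administered to the last 6 patients in the study". Neither names a dose.

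**The concern.** The sponsor foresaw excess toxicity at the starting dose and wrote the first step of the response. The rules after that step were written for a trial that goes from 1 to 10 mg/m². Nothing says that 0.5 mg/m² may be carried into group 3, that 1 mg/m² is closed once the MTD is declared exceeded there, or that the trial stops.

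Safety is the primary objective of this first-in-human study, and group 3 is six of the planned 12–18 patients, a third to a half. The Committee would meet the gap just after two DLTs at the lowest planned dose. It would then have to depart from the written options or have them amended.

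**Working it through.** **1. The plan's own figures.** From the cohort sizes in 3.1 and 3.2, the minimum is 3 + 3 + 6 = 12, the maximum is 6 + 6 + 6 = 18, and the dose-escalation maximum is 6 + 6 = 12. All three agree with 3.2. The sample size is not at fault.

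**2. Tracing the branch.** Suppose two patients at 1 mg/m² have a DLT.
- 1 mg/m² is declared above the MTD (3.1, 5.10).
- Three patients are entered at 0.5 mg/m² (synopsis schema, 3.1, 5.10). Sections 5.3 and 9.3 do not provide for that infusion.
- Suppose at most one of the three has a DLT. On the literal reading, the next three go to the next highest dose, which is 1 mg/m². On the narrow reading, the sentence covers only the move from group 1 to group 2, and no rule applies.
- The interim analysis is triggered by the 10 mg/m² cohort (3.1, 8.4). That cohort should not open, so the trigger does not occur.
- If group 3 were opened all the same, the choice written in 3.1 and 8.4 is 1 mg/m² (declared above the MTD) or 10 mg/m² (ten times that dose).

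Both readings therefore end with no permitted dose below the one declared too high.

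**3. Chance of entering the branch.** The protocol states no DLT rate, so the true rate p at 1 mg/m² is an assumption. With three patients, and three more if exactly one has a DLT:

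P(two or more DLTs) = P(X₃ ≥ 2) + P(X₃ = 1) × [1 − (1 − p)³]

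- p = 0.05: 0.0073 + 0.0193 = 0.0266
- p = 0.10: 0.0280 + 0.0659 = 0.0939
- p = 0.20: 0.1040 + 0.1874 = 0.2914

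**4. Chance that the literal reading points back to 1 mg/m².** Assume the DLT rate q at 0.5 mg/m² lies between p/2 and p, and multiply step 3 by P(at most one DLT in 3 at rate q).
- p = 0.05: 0.0266 × (0.9928 to 0.9982) = about 2.6%
- p = 0.10: 0.0939 × (0.9720 to 0.9928) = 9.1–9.3%
- p = 0.20: 0.2914 × (0.8960 to 0.9720) = 26.1–28.3%

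The rule adding three patients after one DLT refers to either cohort, so it is unclear whether it covers 0.5 mg/m². If it does, the second factor is one minus the step 3 formula evaluated at q. The results become about 2.6%, 8.5–9.1% and 21–26%.

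**5. Sample size if the branch is closed properly.** Up to 6 patients at 1 mg/m² plus 3 at 0.5 mg/m² is 9, and 15 with group 3. If 0.5 mg/m² is also expanded, it is 6 + 6 = 12, and 18 with group 3. The stated maxima still hold.

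**The case against.** The strongest reply is that the protocol does not order re-dosing at 1 mg/m². Section 5.10 defines dose escalation as the move from group 1 to group 2 and bases it on safety. The continuation sentence sits in that text, before 0.5 mg/m² is mentioned, and the sentence after it says that two DLTs mean the MTD is exceeded. The narrow reading is the more natural one, and a sensible Committee would not return to 1 mg/m². This stands. It turns the problem from a harmful instruction into a missing one, but group 3 still has no usable dose.

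A reader might also infer that six patients will be infused above the MTD and count the DLTs expected among them. The documents do not support that. Section 3.2 ties their dose to the interim analysis, whose trigger would not occur, so the branch may simply stall.

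Nor does the text show that a protective change must wait for ethics approval. Section 11.1 requires approval before amendments are implemented, but 10.2 allows an amendment that removes an apparent immediate hazard to take effect at once, with notification and a request for approval as soon as possible.

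The open wording in 3.2 and 5.10 could be said to leave the Committee free to choose 0.5 mg/m². It helps, but 3.1 and 8.4 restrict the same decision to two doses. Section 3.1 also says "The dose selected will be based on imaging characteristics and pharmacokinetic data of" each dose level. It mentions safety in the same context, so safety is not excluded, but no dose is ruled out on safety grounds.

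Finally, the protocol expects little toxicity, cites a no-adverse-effect level about 100 times the starting dose, and does not expect to find an MTD. The branch may well never be used. That limits the size of the problem but does not remove the inconsistency.

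**Conclusion.** The point holds as a conflict among the protocol's stated dose rules in one contingency. After two DLTs at 1 mg/m² the text opens 0.5 mg/m². It then either leads back to a dose declared above the MTD or gives no next step, and in both cases the only doses written for group 3 are that dose and a higher one. It does not establish that patients would in fact be infused above the MTD.

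The chance of reaching the branch is 2.7%, 9.4% or 29.1% at true DLT rates of 5%, 10% or 20%. These rates are assumptions, and the highest has no anchor in the document. Given the primary objective and the very low cost of correction, the rules should be fixed before they are needed, even though 10.2 offers an emergency route.

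**What to change.** In 3.1 and 5.10, state that:
- (a) once two patients at a dose have had a DLT, no further patient in any group is infused at that dose or a higher one;
- (b) the group 3 dose is chosen among doses with at most one DLT, including 0.5 mg/m² if it was opened, and if there is no such dose group 3 does not open;
- (c) the interim analysis follows the last dose-escalation patient, whatever that patient's dose.

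Name 0.5 mg/m² in 5.3, 8.4 and 9.3 so that the infusion and the analysis are provided for. Rule (a) also settles the meaning of the next highest dose.

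The cost is three sentences and three small alignments, with no extra patients, visits or analyses. The downside is confined to this branch: the last six patients would be imaged at 0.5 mg/m², or group 3 would not open.
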